### **Severity of Adverse Event:**

Severity will be categorized using criteria based on CTCAE v.5:

Grade 1 Mild	asymptomatic or mild symptom; clinical or diagnostic observation only; intervention not indicated
Grade 2 Moderate	minimal, local or noninvasive intervention indicated; limiting age-appropriate instrumental ADL
Grade 3 Severe	Severe or medically significant but not immediately life-threatening; hospitalization or prolongation of hospitalization indicated, disabling; limiting self-care ADL
Grade 4 Life-threatening consequences	Urgent intervention indicated
Grade 5 death	Death related to AE

The term "severity" is used to describe the intensity of an event. This is not the same as "serious". Seriousness, not severity, serves as the guide for defining regulatory reporting obligations. The highest severity grade attained should be reported, for AEs with divergent severities.

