**Grades**

Grade refers to the severity of the AE. The CTCAE displays Grades 1 through 5 with unique clinical descriptions of severity for each AE based on this general guideline:

**Grade 1** Mild; asymptomatic or mild symptoms; clinical or diagnostic observations only; intervention not indicated.

**Grade 2** Moderate; minimal, local or noninvasive intervention indicated; limiting age-appropriate instrumental ADL\*.

**Grade 3** Severe or medically significant but not immediately life-threatening; hospitalization or prolongation of hospitalization indicated; disabling; limiting self care ADL\*\*.

**Grade 4** Life-threatening consequences; urgent intervention indicated.

**Grade 5** Death related to AE.

A Semi-colon indicates 'or' within the description of the grade.

A single dash (-) indicates a Grade is not available. Not all Grades are appropriate for all AEs. Therefore, some AEs are listed with fewer than five options for Grade selection.

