#### 5.1.1 Adverse Events

**Non-treatment emergent adverse events** (AEs) will be collected from the time the subject screened into the study (date of signature of informed consent) until first administration of study drug.

Thereafter, all AEs are **treatment-emergent adverse events** (TEAEs) and will be recorded until the end of study visit has been performed. In all outputs, AEs with start date(time) on or after the study drug start date(time) will be considered as TEAEs (i.e., TEAE designation will be programmatically derived based on dates; eCRF checkbox for TEAE will not be used). In case it is impossible to determine whether an AE is treatment-emergent or not (i.e., AE occurs on day 1 but time is unknown), the AE will be considered a TEAE.

Partial start dates of AEs will be imputed according to section [8.1](#) for the determination of non-treatment emergent and treatment-emergent designations.

AEs will be coded based on the Medical Dictionary for Regulatory Activities (MedDRA) latest version available before the database lock. National Cancer Institute's Common Terminology Criteria for Adverse Events (CTCAE) v5.0 will be used for the grading of AEs by the investigators.

For summary tables, AEs with relatedness "Definite", "Probable", and "Possible" will be considered as "Related", AEs with relatedness "Unrelated" and "Unlikely" will be considered "Not Related" and AEs with relatedness "Not Applicable" will be reported as such. AEs with missing relatedness assessment will be considered as "Related" for summary tables and will be footnoted in applicable tables; listings will present relatedness data as collected (i.e., missing).

AEs with missing seriousness assessment will be considered as "Serious" for summary tables; listings will present seriousness data as collected (i.e., missing). Should AEs with missing seriousness be present at time of reporting, these will be footnoted in applicable serious adverse event tables.

AEs with missing severity assessment will be considered as "Grade 3" for summary tables; listings will present severity data as collected (i.e., missing). Should AEs with missing severity be present at time of reporting, these will be footnoted in applicable adverse event tables.

An overall summary of AEs will be produced, including counts and percentages of subjects with any incidence of:

1. AEs (including non-treatment emergent AEs),
2. TEAEs,

3. Non-serious TEAEs,
4. Serious TEAEs (TESAEs),
5. Related TEAEs,

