### 7.2.5 Body of the Data Display

#### 7.2.5.1 Table Conventions

- Units will be included where applicable.
- If the categories of a parameter are ordered, then all categories between the maximum and minimum category should be presented in the table, even if n=0 for all treatment groups in a given category that is between the minimum and maximum level for that parameter. For example, the frequency distribution for symptom severity would appear as:

Severity Rating	n
Very Severe	2
Severe	0
Moderate	8
Mild	3

- If the categories are not ordered (e.g., Medical History, Reasons for Discontinuation from the Study, etc.), then only those categories for which there is at least 1 subject represented in 1 or more groups are required.
- As appropriate, an Unknown or Missing category should be added to any parameter for which information is not available for 1 or more subjects.

- P-values should be output in the format: “0.xxx”, where xxx is the value rounded to 3 decimal places. Any p-value less than 0.001 will be presented as <0.001. If the p-value is returned as >0.999 then present as >0.999.
- Unless otherwise specified, tabular display of data for medical history, prior / concomitant medications, and all tabular displays of adverse event data should be presented by the body system, drug class, or SOC in descending order, assuming all terms are coded. Within the body system, drug class and SOC, medical history (by preferred term), drugs (by ATC code), and adverse events (by preferred term) should be displayed in decreasing order. If incidence for more than 1 term is identical, they should then be sorted alphabetically.
- For categorical summaries (number and percentage of subjects) where a subject can be included in more than one category, a footnote will note if the subject should be included in the summary statistics for all relevant categories or just 1 category and the criteria for selecting the criteria.
- Where a category with a subheading (such as system organ class) has to be split over more than one page, output the subheading followed by “(continued)” at the top of each subsequent page. The overall summary statistics for the subheading will only be output on the first relevant page.

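### The SAP sets every AE with a missing grade to Grade 3, so an ungraded fatal or life-threatening event would be shown too low in the maximum-grade tables

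*SAP*

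**What the plan says.** SAP 5.1.1 (Adverse Events) has investigators grade AEs: "Common Terminology Criteria for Adverse Events (CTCAE) v5.0 will be used for the grading of AEs by the investigators". For a blank grade the rule is that "AEs with missing severity assessment will be considered as 'Grade 3' for summary tables". No condition is attached. Two disclosure steps go with it. Listings keep the grade as missing, and for tables: "Should AEs with missing severity be present at time of reporting, these will be footnoted in applicable adverse event tables".

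The same section treats missing relatedness as Related and missing seriousness as Serious in the summary tables.

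The imputed grade feeds these outputs in SAP 5.1.1:
- overall summary item 7 (TEAEs by maximum CTCAE grade) and the maximum-grade table by SOC, HLGT and PT;
- overall summary items 8 and 9 (Grade 3 or above TEAEs, and the related subset).

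Item 10 of the same summary reports TESAEs leading to death. Each subject is counted once, at the worst level within the MedDRA category.

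The protocol gives the scale in 7.1.1.1 and Appendix 7. Grade 5 is "Death related to AE" and Grade 4 is "Life-threatening consequences; urgent intervention indicated". Section 7.1.1.1 also lists Fatal among the AE outcomes, and death and life-threatening among the seriousness criteria. Section 7.1.1.3 lists seriousness, outcome and severity as separate variables on the SAE form and the eCRF.

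**The concern.** Severity, outcome and seriousness are separate entries, so a grade can be blank while the record already shows that the event was fatal or life-threatening. In that case the grade is missing only in form, because the trial's own definitions fix it at 5 or 4. A rule that ignores those fields puts a value in the table that the rest of the record contradicts.

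The stake is the internal consistency of the safety tables. AE incidence is a primary endpoint, and maximum grade is one of its planned breakdowns. A reader could find a death in one row of the overall summary and no Grade 5 event a few rows above. Deaths are not far-fetched in this population: the protocol background puts death in the late teens or early twenties, and enrolment is at age 17 or older. The boundary between Grades 3 and 4 also attracts attention, because Protocol 11.6 names Grade 4 or higher among conditions that may warrant study termination. The SAP tables do not drive that decision.

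**Working it through.** The plan gives no figure to reproduce. The check applies the rule as written to constructed cases.

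**Inputs**
- N = 6. SAP 2.2 gives six subjects, and SAP 6 reports that six were enrolled and completed titration. All six are taken as the denominator.
- Missing severity = Grade 3 in summary tables (SAP 5.1.1).
- Subject counted once at the worst grade (SAP 5.1.1).
- Fatal = Grade 5, life-threatening = Grade 4 (Protocol 7.1.1.1, Appendix 7).

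**Size of the grading error per event**
- Fatal: 5 − 3 = 2 grades too low.
- Life-threatening: 4 − 3 = 1 grade too low.

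**Effect on the rows.** One subject has a single TEAE, which is ungraded. The other five contribute nothing to these rows.

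| Ungraded event | Row | SAP rule | Using the recorded field |
|---|---|---|---|
| Fatal | Grade 5 | 0/6 (0.0%) | 1/6 (16.7%) |
| Fatal | Grade 3 | 1/6 (16.7%) | 0/6 (0.0%) |
| Fatal | Grade 3 or above | 1/6 (16.7%) | 1/6 (16.7%) |
| Life-threatening | Grade 4 | 0/6 (0.0%) | 1/6 (16.7%) |
| Life-threatening | Grade 3 | 1/6 (16.7%) | 0/6 (0.0%) |
| Life-threatening | Grade 3 or above | 1/6 (16.7%) | 1/6 (16.7%) |
| Neither recorded | Grade 3 | 1/6 (16.7%) | 1/6 (16.7%) |

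The error is confined to the maximum-grade rows. The Grade 3 or above row is the same under both rules, because Grades 3, 4 and 5 all count there.

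**When the subject has other events.** Only the worst grade counts. If the same subject also has an event graded 5, the overall row does not change. If the subject has an event graded 4, an ungraded life-threatening event changes nothing in the overall row, and an ungraded fatal event leaves the subject at 4 instead of 5. The rows for the particular SOC, HLGT or PT can still be wrong if the other event falls under a different term.

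**Consistency of the overall summary.** In the fatal case, item 10 shows 1/6 and the Grade 5 row of item 7 shows 0/6. This assumes that item 10 is taken from the outcome or the seriousness criterion, since the SAP does not name the field.

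**The case against.** The case for leaving the rule alone is strong on frequency and disclosure. Severity is a listed variable for every SAE. Protocol 7.1.1.3 requires active follow-up of missing SAE information, 7.1.1.4 asks for additional information on fatal and life-threatening SAEs within 1 business day, and 9.2 repeats queries until they are resolved. An ungraded death surviving to lock among six subjects is unlikely. If it did, listings would show the blank grade, a footnote would flag it, and the death would have its own row and an entry in the SAE listing. All of this stands and keeps the point small. It does not make the tabulated grade right: a footnote reports that a value was imputed but leaves a value the record contradicts.

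It can also be said that deriving a grade from seriousness blurs two concepts that Protocol 7.1.1.1 keeps apart, and that Appendix 7 notes that Grade 5 does not suit some AEs. That is fair as a general caution. Here the derivation would be only a default for a blank grade, in the two situations where the recorded fact coincides with the grade definition.

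A reader might infer three stronger points, and the documents support none of them.
- *The rule wrongly inflates mild events.* An ungraded mild event does enter the Grade 3 or above rows. That is a defensible conservative choice, in line with missing relatedness and missing seriousness. The literal worst level would be Grade 5, which would impute deaths.
- *The rule breaks the SAP's own table convention.* SAP 7.2.5.1 says "an Unknown or Missing category should be added to any parameter for which information is not available for 1 or more subjects", but the sentence opens with an as-appropriate qualifier and is a general formatting rule. The specific AE rule governs.
- *Some CTCAE terms have no Grade 3.* Appendix 7 says only that "Not all Grades are appropriate for all AEs". It is an extract and does not show a term without Grade 3.

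**Conclusion.** The rule is wrong as written for one narrow class of event: an AE with no grade but a recorded fatal outcome or life-threatening status. Such an event is shown two grades or one grade too low in the maximum-grade summaries, which can move one of six subjects (16.7%) between rows and can contradict the row for TESAEs leading to death. For all other ungraded events, Grade 3 is a reasonable default.

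The severity is minor. It would be tempting to conclude that severe events are under-counted or that the primary safety result changes. The documents do not support this. The Grade 3 or above rows, the incidence of TEAEs and SAEs, and the death row do not depend on the missing grade, and no test or decision rule rests on these tables.

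The conclusion assumes that at least one such grade is still missing at lock (the documents give no expected number), that the subject has no other event already setting the same or a higher maximum, and that life-threatening status can be read from the data. The last is inferred from Protocol 7.1.1.1 and 7.1.1.3, because the CRF is not among the documents.

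**What to change.** Replace the rule in SAP 5.1.1 with: *For summary tables, an AE whose severity is missing will be counted as Grade 5 if its recorded outcome is fatal, as Grade 4 if it is not fatal but is recorded as life-threatening, and as Grade 3 otherwise.* Keep the existing listing and footnote rules unchanged. No separate row for missing grades is needed.

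The cost is one sentence in the SAP and one condition in the derivation program, using fields the protocol already has recorded. The Grade 3 or above counts stay as they are. If the CRF does not hold life-threatening status as a separate field, that condition would have to be read from the SAE form or left out. The fatal-outcome condition would still remove the conflict with the death row.

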### **5.1.2 Clinical Laboratory Tests**

Hematology, biochemistry, and urine results will be reported using standard units as provided by central laboratory; no further standardization is applied by [REDACTED].

Lab values below lower limit of quantification (LLOQ) will be imputed as  $\frac{1}{2}$  LLOQ. Lab values above upper limit of quantification will (ULOQ) will be imputed as  $1.1 * \text{ULOQ}$ .

The following clinical laboratory evaluations will be reported:

1. **Hematology:** hemoglobin, hematocrit, erythrocytes, leukocytes, differential white blood cell count, thrombocytes.
2. **Biochemistry:** creatinine, total bilirubin (direct and indirect if values were above normal ranges), hemoglobin A1c (HbA1c), alkaline phosphatase, aspartate aminotransferase, alanine aminotransferase, gamma glutamyl transpeptidase, creatinine kinase, sodium, potassium, cholesterol (total, HDL, LDL), triglycerides, creatinine clearance.
3. **Urine:** glucose, nitrate, pH, hemoglobin, leukocytes, specific gravity, protein, ketones.
4. **Other tests:** HIV, hepatitis B, hepatitis C.
5. **Pregnancy test:** urine/serum.

Observed values and changes from baseline for hematology and biochemistry will be summarized at each scheduled post-baseline visit. Baseline will be defined as last value collected before first study drug administration (both dates and times will be compared); both data collected at scheduled and unscheduled visits will be included in baseline derivation.

Additionally, shift tables from baseline to each scheduled post-baseline visit will be added for select laboratory parameters: thrombocytes, and creatinine kinase. Lab values will be classified as low, normal, and high for the purpose of shift table creation.

Urinalysis overall interpretation (Abnormal – Clinically Significant / Abnormal – Not Clinically Significant / Normal) will be presented by visit in a frequency table. Urinalysis results by parameter will only be listed.

Laboratory data will be listed.

### 5.1.3 12-Lead Electrocardiogram

Electrocardiogram (ECG) results collected through the study include:

1. PR interval (msec),
2. QRS duration (msec),
3. RR interval (msec),
4. QT interval (msec),
5. QTcF (msec),
6. Overall interpretation (Normal / Abnormal – Not clinically relevant / Abnormal - Clinically relevant).

QTcF will be presented as collected on eCRF (i.e., no derivations done by [REDACTED] biostatistics).

Observed values and changes from baseline for continuous ECG parameters will be summarized at each scheduled post-baseline visit; overall interpretation results will only be listed.

When triplicate values are collected at given visit, the average of the triplicate will be calculated and presented for that visit; in case less than three values are reported, the average will be calculated over non-missing values. Baseline for ECG is based on averaging the last pre-dose triplicate (not the last individual measurement pre-dose).

All ECG data will be listed (including the individual triplicate measurements as well as the average results).

#### **5.1.4 Slit Lamp Evaluation**

Slit lamp evaluation results collected through the study include:

1. Ocular cataracts performed (Yes / No) and result, if performed (Normal / Abnormal),
2. Ocular opacity performed (Yes / No) and result, if performed (Normal / Abnormal).

Slit lamp evaluation results will be presented by visit in a frequency table.

Slit lamp evaluation data will be listed.

#### **5.1.5 Vital Signs and Body Measurements**

Vital signs (VS) and body measurements results collected through the study include:

1. Height (cm; only collected at screening),
2. Weight (kg),
3. BMI ( $\text{kg}/\text{m}^2$ ),
4. Systolic blood pressure (mm Hg),
5. Diastolic blood pressure (mm Hg),
6. Heart rate (beats per minute).

For screening visit, BMI auto-calculated in the eCRF will be used. For other visits where weight is measured, BMI will be calculated by [REDACTED] biostatistics as:

$$\text{Weight at Given Visit in kg} / (\text{Baseline Height in m})^2.$$

Observed values and changes from baseline for VS and body measurements parameters (excluding height) will be summarized at each scheduled post-baseline visit. Baseline will be defined as last value collected before first study drug administration (both dates and times will be compared); both data collected at scheduled and unscheduled visits will be included in baseline derivation.

For weight, percent change from baseline will additionally be included in the summary tables.

VS data will be listed.

#### **5.1.6 Physical Examination**

The following body systems are assessed through the study:

1. General appearance, skin, neck (including thyroid),
2. HEENT (head, ears, eyes, nose, throat),

3. Cardiovascular,
4. Respiratory,
5. Abdomen,
6. Lymph nodes,
7. Extremities,
8. Nervous system,
9. Musculoskeletal.

For each of the body systems, the result is assessed as Normal / Abnormal – Clinically significant / Abnormal – Not clinically significant.

Physical examination results will be summarized by body system and visit in a frequency table.

Physical examination data will be listed.

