Adverse events	X	X	X	X	X	X	X	X	X
Telephone follow-up by TCH PI C					X				X
Laboratory Assessments									
Pregnancy test (females) D	(X)					X			
Chemistry E	(X)					X			
Hematology F	(X)					X			
Urinalysis G	(X)					X			
Study Drug Administration									
Miglustat dose H	X	X	X	X	X	X	X	X	X
Miglustat supplied I	X	X	X	X	X	X	X	X	X
PK									
Draw blood	X J								X K
Efficacy Assessments									
Seizure diary collection L					X				X
Seizure diary dispensation					X				X

A An abbreviated physical examination will assess only the general appearance of the patient and is only required when a complete exam is not indicated.

- B Vital signs include systolic and diastolic blood pressure [sitting for 5 minutes] and pulse rate.
- C The TCH PI will conduct monthly telephone safety check-ins during the dose-titration period and every 2 to 4.5 months thereafter to discuss AEs and concomitant medications. If the subject cannot be reached, TCH will contact the Local Health Center to organize the call.
- D Urine test is acceptable. If first dosing visit is scheduled > 28 days after the NIH visit, pregnancy test should be repeated within 7 days prior to the first dosing visit
- E Chemistry laboratory parameters include HbA1c, creatinine, total bilirubin (direct and indirect if values were above normal ranges), alkaline phosphatase, aspartate aminotransferase, alanine aminotransferase, gamma glutamyl transpeptidase, creatine kinase, sodium, potassium, cholesterol, and triglycerides. Those tests are to be repeated prior to the first dosing visit only if first dosing visit is scheduled >42 days after the TCH visit.
- F Hematology laboratory parameters include hemoglobin, hematocrit, erythrocytes, thrombocytes, and white blood cell count with differential (for an absolute neutrophil count, lymphocyte count and monocyte count). Those tests are to be repeated prior to the first dosing visit only if first dosing visit is scheduled > 42 days after the TCH visit.
- G Dipstick urinalysis includes glucose, nitrate, hemoglobin, leukocytes, protein, pH, ketones, and specific gravity. If first dosing visit is scheduled > 42 days after the TCH visit, safety labs should be repeated prior to the first dosing visit.

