### **8.7 Safety Analyses**

All subjects who enroll in the study and receive at least 1 dose of study medication will be included in the safety population. Safety will be evaluated by AEs, clinical laboratory tests, vital signs, ECGs, slit lamp evaluation and physical examinations. Safety data will be summarized using descriptive statistics by visit or timepoint, as appropriate. Treatment-emergent AEs and SAEs will be tabulated and summarized by system organ class, preferred term, severity, and relationship to study drug.

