**Table 1. Study Objectives and Endpoints**

Objectives	Endpoints
Primary	

 
To assess the safety and tolerability of the Batten-1 treatment regimen over the study period
 
	
 
Incidence of treatment-emergent adverse events (TEAEs) and serious adverse events (SAEs);
 
Changes from baseline in clinical laboratory tests (hematology, chemistry, and urinalysis), 12-lead electrocardiogram (ECG) findings, slit lamp evaluation, vital signs (heart rate and blood pressure) as well as physical and neurological examinations
 

Secondary	

 
To assess the pharmacokinetics (PK) of miglustat in subjects with CLN3 disease
 
	
 
Week 1 first dosing: Maximum plasma concentration (Cmax), Time to Cmax (Tmax), area under the concentration-time curve calculated to the last observable concentration at time t (AUC 0-t), area under the concentration-time curve extrapolated to infinity (AUC 0-∞), elimination half-life (T1/2)
 
Week 9 - Repeated dose (steady state): Cmin, Cmax, Tmax, AUC 0-8hr
 

 
To assess the effect of the Batten-1 treatment regimen on the longitudinal progression of clinical symptoms of CLN3 disease
 
	
 
Unified Batten Disease Rating Scale (UBDRS)
 
Seizure frequency (diaries)
 
Vineland Adaptive Behavior Scales, Version 3 (Communication, Daily Living Skills, Socialization, and Motor Skills domains)
 
Ophthalmic assessments including visual acuity, visual fields (if feasible), and optical coherence tomography (OCT)
 
Magnetic resonance imaging (MRI)
 

Exploratory	

 
To assess potential biomarkers of CLN3
 
	
 
Measure biomarkers in cerebrospinal fluid (CSF), blood and urine and CSF concentration of miglustat
 

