### **5.1.7 Neurological Examination**

Neurological examination results collected through the study include:

1. Visual impairment assessment performed and result, if performed,
2. Mental status assessment performed and result, if performed,
3. Cranial nerves function assessment performed and result, if performed,
4. Motor function assessment performed and result, if performed,
5. Sensory function assessment performed and result, if performed,
6. Cerebellar function assessment performed and result, if performed.

For each assessment performed, the result is assessed as Normal / Abnormal.

Neurological examination results will be presented by visit in a frequency table.

Neurological examination data will be listed.

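### Four components of the primary safety endpoint are worded as changes from baseline, but their planned by-visit tables do not in general show how many subjects changed

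*SAP*

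**What the plan says.** SAP Table 1 lists as primary endpoints "Changes from baseline in clinical laboratory tests (hematology, chemistry, and urinalysis), 12-lead electrocardiogram (ECG) findings, slit lamp evaluation". The same entry goes on to vital signs and to the physical and neurological examinations. The protocol synopsis has the same components.

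The planned summaries are:

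- Slit lamp (SAP 5.1.4; 2 items, Normal/Abnormal): "Slit lamp evaluation results will be presented by visit in a frequency table".
- Physical examination (SAP 5.1.6; 9 body systems, three levels): "Physical examination results will be summarized by body system and visit in a frequency table".
- Neurological examination (SAP 5.1.7; 6 domains, Normal/Abnormal): "Neurological examination results will be presented by visit in a frequency table".
- Urinalysis (SAP 5.1.2): the overall interpretation, on three levels, "will be presented by visit in a frequency table. Urinalysis results by parameter will only be listed".

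All of these are also listed. Elsewhere the SAP does tabulate change. Hematology, biochemistry, continuous ECG parameters and vital signs have change-from-baseline summaries, and "shift tables from baseline to each scheduled post-baseline visit will be added for select laboratory parameters", namely thrombocytes and creatine kinase (which the SAP calls creatinine kinase). Protocol 8.7 is general: "Safety data will be summarized using descriptive statistics by visit or timepoint, as appropriate".

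**The concern.** A by-visit frequency table gives the number abnormal at each visit, not who they are. If one subject becomes abnormal while another returns to normal, the count stays the same. For these four components, therefore, no planned table reports the endpoint as it is worded.

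The two examinations and the slit lamp are there to detect change within a subject. Protocol 2.3.1.1 asks for baseline and roughly six-monthly neurological evaluation because of peripheral neuropathy reported with miglustat. Protocol 7.1.7 gives monitoring of cataract and opacity as the purpose of the slit lamp. At stake is whether the report can state, item by item, how many subjects normal at baseline became abnormal, or whether the reader must work it out from listings.

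**Working it through.** **Inputs.** N = 6 (SAP 2.2). Item counts and levels are as listed above. The post-baseline site visits are Weeks 26, 52, 78 and Visit 6 (Protocol Table 1-2). The plan gives no power, alpha or precision figure to reproduce. The baseline counts are not in the documents, so all possible values are shown.

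**1. One binary item, one visit, complete data.** Let b be the number abnormal at baseline and f the number at the visit. The number newly abnormal lies between max(0, f − b) and min(f, 6 − b).

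- b = 3, f = 3: max(0, 0) = 0 to min(3, 3) = 3.
- b = 2, f = 3: max(0, 1) = 1 to min(3, 4) = 3.
- b = 0, f = 2: 2 to min(2, 6) = 2, so it is fixed.
- b = 6, f = 6: 0 to min(6, 0) = 0, so it is fixed.

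**2. All 7 × 7 = 49 pairs (b, f).** The width of the range is min(b, f, 6 − b, 6 − f). It exceeds zero only when b and f both lie between 1 and 5, which is 5 × 5 = 25 pairs. The width is 1 in 16 pairs, 2 in 8 and 3 in one; the other 24 pairs are fixed.

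| Abnormal at baseline | 0 | 1 | 2 | 3 | 4 | 5 | 6 |
|---|---|---|---|---|---|---|---|
| Open visit counts, of 7 | 0 | 5 | 5 | 5 | 5 | 5 | 0 |
| Largest width (subjects) | 0 | 1 | 2 | 3 | 2 | 1 | 0 |

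**3. Ever newly abnormal over four visits.** Baseline 0/6 followed by 1/6 at every visit fits 1 subject (the same one each time) to 4 (a different one each time). If abnormalities never revert, complete data fix the number newly abnormal at a visit at f − b. Even then, one missing subject opens it by 1: 1/6 then 1/5 fits 0 if the missing subject was normal at baseline, and 1 if that subject was the abnormal one.

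**4. Three-level items.** Six subjects in three levels give 28 count vectors and 28 × 28 = 784 pairs. There are a + 1 vectors with a abnormal, so the number newly abnormal is open in (2 + 3 + 4 + 5 + 6)² = 20² = 400 pairs. Enumerating all 3 × 3 transition tables leaves the number worsened open in 550 pairs. For example, 2/2/2 at both visits fits 0 to 2 newly abnormal and 0 to 4 worsened.

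The figures in steps 2 and 4 count possible tables. They are not probabilities.

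**5. Baseline, if change is tabulated.** Slit lamp and neurological examination have one scheduled pre-dose assessment, at Visit 2. Complete physical examinations are scheduled at Visits 1 to 6, of which two (Visits 1 and 2) are pre-dose. Abbreviated ones are scheduled on Day 1 and Weeks 5 and 9 (Table 1-3), Weeks 10, 14, 22, 34 and 42 (Table 1-4), and Weeks 58 and 70 (Table 1-5): 3 + 5 + 2 = 10. Two more, at Weeks 82 and 94, depend on treatment duration after Week 78. The protocol says of these examinations: "An abbreviated physical examination will assess only the general appearance of the patient and is only required when a complete exam is not indicated". SAP body system 1 combines general appearance with skin and neck. A shift table for physical examination therefore has to say which examination is the baseline.

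**The case against.** **The SAP follows the protocol's statistics section.** This stands. Protocol 8.7 asks for descriptive summaries by visit, and the endpoint text does not define change as a count of newly abnormal subjects. A reader might infer that the SAP departs from the protocol's planned analysis; it does not. The mismatch is with the endpoint wording alone.

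**With six subjects the listings suffice.** Largely true. SAP 5.12 sorts listings by subject and then visit, so each sequence can be read directly. No data are lost, and no test or decision rule uses these tables. What remains is that the reader must choose the baseline and handle missing and unscheduled results unaided.

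**Adverse changes are already counted.** For physical examination, Protocol 7.1.6 sends any adverse change from baseline to the AE page, and its scope includes the nervous system. Clinically relevant laboratory changes also become AEs (7.1.1.5). But SAP 5.1.1 counts AEs by MedDRA term, not by examination item, and gives no denominator of subjects normal at baseline.

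**The missing baseline rule is a second defect.** A reader might infer this from SAP 5.1.6. The documents do not support it, because neither planned physical-examination output uses a baseline; the rule is needed only once change is tabulated. Nor is the timing of the Day 1 examination wholly open. For home visits, Appendix 8 has assessments completed and relayed before the dose is decided. Timing is unstated only for visits at a local health center.

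**Abbreviated results contaminate body system 1.** This cannot be established. It depends on how the CRF records them, and the CRF is not among the documents.

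**Conclusion.** The point holds as a mismatch between the endpoint wording and the planned tables for four components, covering 18 parameters (9 body systems, 6 neurological domains, 2 slit-lamp items and the urinalysis interpretation). For a binary item at one visit, by-visit counts leave the number newly abnormal open by at most 3 of 6 subjects, and by none when everyone or no one is abnormal at baseline. The 25 of 49 figure must not be read as a chance that the tables will be uninformative.

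The practical size depends on baseline counts that the documents do not give. CLN3 disease is progressive, with total vision loss typically 2–3 years after onset at ages 4–7 (Protocol 2.2), and subjects are at least 17. Some neurological items may therefore be abnormal in five or six subjects at baseline; the gain there is at most one subject or none. It is larger for items with mixed baseline status, or where abnormalities come and go.

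This is a cheap improvement worth making. It does not show that the primary safety objective cannot be assessed.

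**What to change.** 1. Add baseline-by-visit shift tables for slit lamp, neurological examination, physical examination (complete examinations only) and urinalysis interpretation, at Weeks 26, 52, 78 and Visit 6, with Week 6 added for urinalysis. Include a Missing row and a worst-post-baseline column. State that this column takes in unscheduled assessments, because SAP 5.12 otherwise keeps them out of summary tables. For physical examination and urinalysis it should also take in the premature-discontinuation visit.
2. A lighter alternative is n/N newly abnormal among those Normal at baseline, with a Missing row and the same worst-post-baseline column. It loses movement between the two abnormal levels of physical examination and urinalysis.
3. As part of the same change, apply the last-pre-dose rule already in SAP 5.1.2 and 5.1.5. For physical examination, use the last complete pre-dose examination. List abbreviated results, and keep them out of the body-system 1 row if the CRF records them there.
4. Footnote that worsening of an item already Abnormal at baseline cannot be seen on a binary scale.

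**Cost.** No new data, and the by-visit tables stay. With five columns (six for urinalysis), the full version has 9 × 9 × 5 = 405 cells for physical examination, 6 × 4 × 5 = 120 neurological, 2 × 4 × 5 = 40 slit lamp and 9 × 6 = 54 urinalysis, or 619 before Missing rows. That is bulky for six subjects. The lighter version has 17 × 5 + 6 = 91 entries before Missing rows, some with a denominator that may be 0 or 1.
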